### **Optional Sub-study (UNC Only)**

#### *Ecological Momentary Assessment*

Ecological Momentary Assessment (EMA) allows for the acquisition of naturalistic, real-time assessment of participants' self-reported mood, activities, and behaviors. *Study Procedures*-At the first MRI visit in the BRIC, the subject will review the UNC econsent form that contains the description of this EMA portion of the study. They will either choose to participate or not participate by indicating so on the consent (and can only possibly participate if they have an android or iPhone themselves). If they do agree to participate, at the end of the MRI session, the researcher will guide the participant in downloading the app to the participant's smartphone. The researcher will provide orientation to the app and answer any questions regarding the EMA assessments and data collected. The participant will need to provide an email address & password to be able to access the study specific application. MetricWire will then automatically assign them a unique ID. The EMA data (EMA specific questions are attached to the amendment application for review) will be collected over the course of four 5-day blocks (Saturday-Wednesday) following each of four MRI sessions (during weeks 1, 9, 13, and 16, if applicable).

Since the 1st phase of the study entered a R61 no cost extension & due to limited funds, participants no longer received up to 4 scans. Participants received only pre- and post-treatment scans (2 scans total) &

thus only do EMA after pre & post MRI scans. This is true for any participant who signs the UNC consent on or after 11/1/18 as part of R61.

**R33: The study has entered the R33 phase and with funds available, participants will have the option of participating in the EMA portion after the pre and post treatment scan visits as well as after wks 4, 8, and 12 (if applicable) after completing the computer task visit. These participants will follow the same prompt schedule as pre and post scan EMA timepoints.**

There will be 2 EMA assessments per day on weekdays and 3 per day on weekends. EMA assessments will occur between 9am on Saturday and 9pm on Wednesday, at specified time windows distributed throughout the day (e.g., 4-7pm). No contact will be made on weekdays between working hours of 9-5. Participants who work outside of these hours will be given the option to block off their unavailable work time. At each EMA timepoint, an alert will be sent to the participant's smartphone (iPhone or Android) and they will be instructed to answer questions regarding current affect, anhedonia (both anticipatory and consummatory), stress, cognitions, and recent activities. EMA data will be collected using the *MetricWire* application. All EMA data will be encrypted on participants' smartphones prior to being uploaded to a secure server and downloaded by the researcher to UNC CIDD secure server in the study specific folder.

In this EMA portion of the study, we will be using **Passive Location Tracking (PLT)** to monitor patient movement during the 5 days (Saturday 9am-Wednesday 7pm) after each MRI. PLT allows us to compare distance traveled before and after both treatments as a secondary, exploratory measure of behavioral activation. With PLT, the server pings the subjects phone to collect a specific GPS location to set up a fence and then only when the phone moves outside of this location, will it wake up & send another GPS location back to MetricWire services. PLT uses what they call the **Geofencing API of the Android or iOS** operating system to do the monitoring of location changes by the participant. More specifically, once these fences are set, the app waits for the system to notify it that the device has left the specified fence. At this time, the app wakes up, determines and records its new location, updates the fences to center on its new location and returns to the inactive state.

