## 6 STUDY INTERVENTION

### 6.1 STUDY INTERVENTION(S) ADMINISTRATION

#### 6.1.1 STUDY INTERVENTION DESCRIPTION

##### **Behavioral Activation Treatment for Anhedonia (BATA)**

Treatment in the R61 phase (Phase I) will consist of up to 15 weekly 45-minute sessions. This duration maybe modified in the R33 phase as a result of R61 phase Aim 2 analyses. Update for R33: Duration will remain as 8-15 weeks of treatment. Session 1 provides orientation and psychoeducation on anhedonia, and activity monitoring is introduced. Sessions 2-3 include structured values assessments of 10 life areas (e.g., Family Relationships, Employment/Career) to enhance motivation for sustained behavior change and to clarify goals. Following goals clarification, an activity hierarchy is developed, establishing a set of idiographic behavioral targets across life areas prioritized by ease of implementation to scaffold task engagement during the course of treatment. Session 4 focuses on reduction of avoidance. Sessions 5 and above assess completion of goals from the previous sessions, troubleshoot barriers to goal completion, and assign goals for the coming weeks. In the R33 phase, the minimum number of sessions will be 8 to allow for all planned content to be introduced, with a maximum of 15 sessions. Inherent in this structure is therapist assistance in setting achievable goals, which is often impaired in the context of anhedonia. Embedded in the review of goal completion is heightened awareness of anhedonia and identification of behaviors that are associated with greater positive response in the form of subjective importance and enjoyment. Those behaviors then form the basis of goals for the following weeks. The therapist uses motivational techniques to elicit goal-directed behaviors outside session including tying goals to the patient's identified values, open-ended questioning and reflective listening, and functional analysis to select behaviors maximally likely to achieve the patient's goals. Increased positive affect and decreased negative affect are theorized to result from increased contact with potential reinforcers through reduced behavioral avoidance. Maladaptive behaviors such as avoidance decrease the effectiveness of positive events in shaping future behavior, weakening the learned association between adaptive behaviors and positive outcomes. In this way, the overarching goal of BATA is to encourage the

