#### **6.1.2 DOSING AND ADMINISTRATION**

##### **MBCT/BATA Therapy Window Visits:**

Therapy sessions will be managed overall by calendar weeks, rather than trying to count days. This study is offering up to 15 weeks (as opposed to sessions) of treatment. Therapists will be instructed that they need to push to schedule at least one appointment per week, even if it's not on the same day of the week each week. The therapy portion of the study will follow this protocol:

Therapy Week	Procedures & Window
Week 0	The week the first MRI scan takes place. This "starts the clock" for both therapy and assessments
Weeks 1-3	Weekly therapy sessions. Sessions can start post-scan in week 0 if preferred; up to two sessions can be scheduled in a calendar week to make up missed sessions, with no more than three sessions completed by the end of week 3. Therapy content will not be skipped: for example, the content designated for Session 1 will be administered at the first therapy session, regardless of the week in which it takes place.
Week 4	Follow-up REDCap Questionnaires, computer tasks, and therapy. REDCap questionnaires and computer tasks will take place in this week as long as at least one session was attended in weeks 0-3. If 0 sessions were attended prior to this week, assessment is delayed to Week 5. If a subject has not attended at least one therapy session by the end of Week 4, they are a study drop by the 4-miss rule. This way every subject will have at least one "dose" (=therapy session) prior to the Wk4 visit.
Week 5	Weekly therapy session. If necessary, this can be a make-up for the Week 4 assessment if they did not attend or if Week 4 was first therapy session. If the participant does not attend therapy in Weeks 4 or 5, the "Wk4 Assessments" will not be collected and will be considered missing.
Weeks 6-7	Weekly therapy sessions. Up to two sessions per week can be conducted to make up previous missed appointments. No more than 7 Sessions will be delivered by the end of Week 7.
Week 8	Follow-up REDCap questionnaires, computer tasks, therapy, MRI Scan. If the subject has not attended at least 2 sessions overall, including at least 1 session in weeks 5-7, assessments and MRI scan may be delayed to Week 9. If a subject has not attended at least 1 session between weeks 5-8, they are a study drop by the 4-miss rule. Clinical response will be assessed and discussed with participants at this therapy session to determine if therapy is complete or will continue.

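### The first EMA and location-tracking block is not guaranteed to precede therapy Session 1, so some participants' pre-treatment records may be partly or wholly on treatment

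*Combined protocol and SAP*

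**What the plan says.** - **EMA calendar.** Section 4.2 (Ecological Momentary Assessment) sets 5-day blocks, Saturday to Wednesday, "following each of four MRI sessions (during weeks 1, 9, 13, and 16, if applicable". For the R33 phase it adds blocks after the week 4, 8 and 12 task visits: "These participants will follow the same prompt schedule as pre and post scan EMA timepoints". In both phases the first block follows the pre-treatment scan.
- **Location tracking.** It runs over the same five days after each MRI. Its stated use: "PLT allows us to compare distance traveled before and after both treatments as a secondary, exploratory measure of behavioral activation".
- **Therapy calendar.** Section 6.1.2 defines week 0 as the week of the first scan and schedules weekly sessions from week 1, "with no more than three sessions completed by the end of week 3". It also says "Sessions can start post-scan in week 0 if preferred". A drop provision in the same table sets the latest permitted start: "If a subject has not attended at least one therapy session by the end of Week 4, they are a study drop by the 4-miss".
- **Session content.** For BATA, Section 6.1.1 says "Session 1 provides orientation and psychoeducation on anhedonia, and activity monitoring is introduced". MBCT opens with core meditation practice and has daily home practice and logging, included to match BATA's homework and monitoring.
- **Analysis.** Section 9.2 names hierarchical linear modeling for the EMA waves. It gives no time origin and no rule for sessions received before or during the first block.

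**The concern.** EMA Aim 3 asks whether BATA, relative to MBCT, improves real-world positive affect and use of BATA skills. EMA Aim 4 relates fMRI change to those outcomes. The distance comparison is explicitly before against after treatment. All three need an untreated starting value, and the first block is the only candidate.

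That block shares its week with scheduled therapy and can follow a permitted Session 1. Randomization is listed after the pre-treatment scan (Section 4.1, Study Visits), and participants know their arm (Section 6.3), so records made after Session 1 are both exposed and unblinded. BATA Session 1 introduces activity monitoring, while the EMA prompts ask about recent activities and the protocol intends EMA to capture BATA skills (Section 2.3.2). In Aim 4, a 7T baseline taken before therapy could be paired with an EMA baseline that is partly on treatment. Section 9.1 says the EMA data may be used to estimate effect sizes for future applications, so a distorted baseline could carry into later designs.

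**Working it through.** The plan gives no figure for this point, so the check lays the two calendars side by side and counts prompts.

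**Inputs.** From Section 4.2: 3 prompts per weekend day, 2 per weekday, Saturday 9am to Wednesday 9pm, and no weekday contact between 9 and 5. From Section 6.1.2: the week-0 definition and the therapy windows.

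**Reading adopted.** The scan is on a weekday and the block starts on the first Saturday after it, so its three weekdays are Monday to Wednesday of week 1. A week-0 session is taken to fall after the scan and before that Saturday. A week-1 session falls on a weekday.

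**Prompts per block.** 3 + 3 + 2 + 2 + 2 = 12, of which 6 are on the weekend.

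**Prompts after Session 1.** On the day of the session, 0, 1 or 2 of that day's prompts may follow it. Each later weekday in the block adds 2. The last column is the weekend share of the prompts left before Session 1.

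| Session 1 | Prompts after it, of 12 | Weekend share of the rest |
|---|---|---|
| Week 0, after the scan | 12 (100%) | no prompts left |
| Monday, week 1 | 4 to 6 (33-50%) | 6/8 = 75% to 6/6 = 100% |
| Tuesday, week 1 | 2 to 4 (17-33%) | 6/10 = 60% to 6/8 = 75% |
| Wednesday, week 1 | 0 to 2 (0-17%) | 6/12 = 50% to 6/10 = 60% |
| Thursday, Friday or later | 0 | 6/12 = 50% |

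**Average share.** The documents give no distribution of start dates. Assume first sessions are spread evenly over Monday to Friday of week 1:

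- both same-day prompts before the session: (4 + 2 + 0 + 0 + 0)/(5 × 12) = 6/60 = 10%
- one before and one after: (5 + 3 + 1 + 0 + 0)/60 = 9/60 = 15%
- both after: (6 + 4 + 2 + 0 + 0)/60 = 12/60 = 20%

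Week-0 starts raise this average, and starts in weeks 2 to 4 lower it.

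**Effect on a change score (illustration only).** Let the true change in an arm be Δ. Let a share s of baseline prompts be exposed, and let a fraction f of Δ already be present in them. The baseline mean rises by s·f·Δ, so the measured change is Δ(1 − s·f). With f = 0.3:

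- s = 0.25 keeps 1 − 0.075 = 92.5%
- s = 0.5 keeps 1 − 0.15 = 85%
- s = 1 keeps 1 − 0.30 = 70%

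For BATA minus MBCT with the same s in both arms, the error is −s(f_B·Δ_B − f_M·Δ_M). It is zero if the early shifts are equal, and its sign depends on which arm moves more after its first session. The documents give none of s, f or Δ.

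**The case against.** The strongest reply is that overlap is permitted, not shown. Week-0 sessions are optional, week 1 has no fixed therapy day, and the first session can slip to week 4. Anyone starting on Thursday or Friday of week 1, or later, has a clean block, and the six weekend prompts precede any weekday session in week 1. This stands. A reader might infer that the baseline is contaminated for everyone; the documents do not support that.

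A reader might also infer that the flaw sits in the BATA arm and shrinks the BATA effect. That does not follow either. MBCT has homework and logging by design, so both arms are exposed. BATA Session 1 is orientation, psychoeducation and the start of monitoring. Values work, avoidance reduction, initiation of new behaviors and savoring come in Sessions 2 to 6. Whether the first session moves affect, skill use or distance within days, and in which arm more, cannot be derived.

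It is also fair to say that the hierarchical model is described too briefly to fault its time origin, that the EMA items are in an attachment not in the document, and that these are optional, exploratory or preliminary aims. The SHAPS, task and fMRI baselines are placed before therapy, and the go/no-go decision rests on fMRI regions of interest alone.

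None of this supplies the missing rule. The protocol does tie the pre-treatment PET scan to therapy, requiring it before the third session (Section 4.2). It sets no such limit for EMA or location tracking.

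**Conclusion.** The point holds in a limited form. The protocol does not ensure that the first EMA and location-tracking block precedes Session 1, and the plan as written would count exposed records as pre-treatment. Exposure per participant runs from 0 to 12 of 12 prompts: all 12 for a week-0 start, up to 6 for a Monday start, none for a Thursday, Friday or later start. An average of 10-20% rests on the assumption of first sessions spread evenly over the weekdays of week 1; the actual figure depends on session dates the documents do not give.

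The gap exists in both R61 and R33. It affects EMA Aims 3 and 4 and the exploratory distance comparison, and no primary endpoint. The size and direction of any bias are unknown. It deserves correction because it can be settled with a rule fixed in advance, not because a conclusion is known to be wrong.

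**What to change.** Add the following to the EMA part of Section 9.2 before the EMA data are analyzed, so that the baseline is not chosen after results are seen:

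1. Merge the EMA and location time stamps with the recorded date and time of Session 1.
2. Define baseline as records made before Session 1.
3. Code later week-1 records as early-treatment observations in the hierarchical model.
4. Include a weekday/weekend term, and for distance compare like days. Truncation shifts the baseline toward weekends: for a Monday start, 75-100% of the remaining prompts are weekend prompts, against 50% in a full block. Without this term the rule would confound change with day of week.
5. Keep participants with no record before Session 1 in the model, without a baseline wave.
6. Apply the same baseline rule to the EMA change used in Aim 4.
7. Report by arm how many participants and prompts are affected, and give a sensitivity analysis that uses the full first block.

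**Cost.** A few lines of analysis text and a date merge. EMA enrollment has ended, so no visit or procedure changes. Therapist session notes are entered in REDCap (Section 10.1.9.1); the fix assumes that these, and the app records, carry usable dates and times. The downside is fewer baseline prompts and less precision for early starters.

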#### **Optional Sub-study (UNC Only)**

**PET Scan (Pre and possibly Post) \*\*As noted above, this optional PET sub-study completed the last T2 PET scan on 7/7/21 and is no longer enrolling new participants and no additional participants are pending a final PET scan.**

Equipment: The Biomedical Research Imaging Center (BRIC) utilizes a research-dedicated Siemens Biograph mMR whole-body imaging system for PET/MR data collection. The Siemens Biograph mMR allows for simultaneous acquisition of MR and PET images to produce high resolution images in addition to displaying cell metabolism and molecular events.

As part of the NIMH supplement, subjects who meet the inclusion/exclusion criteria for the main study as assessed at Duke and at UNC in the BRIC per the MRI checklist, will be offered the PET sub-study consent at their first appointment at UNC. If the subject has had a PET scan in the last 1 year or has been treated with radiation or chemotherapy in the last 2 months, they will not be eligible to participate in the sub-study. The BRIC tech will also complete the PET checklist with the subject to confirm final eligibility for the subject. The PET scan can be done on the same day as the blood & 7T fMRI and will add about 2-2.5 hours to the visit, if they sign the PET consent. If preferred, the PET scan can be scheduled for a separate day after this initial UNC blood and 7TMRI visit at their convenience. We will allow the PET scan to be completed anywhere before their 3rd therapy session at Duke. The PET scan visit done separately will be

~2.5 hours and the actual scan is about 75 minutes. Their possible post PET scan will be scheduled after their last therapy session at Duke and can be done on the same day as their blood & fMRI or separately, and we will aim to do this within 4 weeks of completing therapy.

*On the day of the PET scan (if separate from 7TfMRI):* After arrival at the BRIC, participants will undergo a final PET/MR screening and the scan, conducted by BRIC's imaging staff. As part of the final screening procedures, participants will be reassessed by the BRIC technologist for any potential adverse outcomes of the scan. If any concerns are raised, participants will not undergo the scan. Instead, participants will be informed of this decision and thanked for their time. Alternatively, if participants are cleared, they will begin out-of-scanner training in preparation for the scan.

**Out-of-Scanner Training (~15 minutes):** Participants will practice the Monetary Incentive Delay (MID) on a computer in a separate, private room prior to the actual scan. This practice session will familiarize participants with the computer task to be completed in the scanner.

***Radiotracer Injection and PET/MR Scan:*** After the out-of-scanner training, participants will be escorted to a private room in which they will be asked to change into a pair of clean scrubs provided by the BRIC. They will also be asked to remove any loose objects (e.g., watches, jewelry, and cellphones) that may interfere with scanning and secure their belongings in a secured locker only accessible to the participant. A trained BRIC technician will reiterate the requirements for the scan (e.g., remain still, remove jewelry and any other metallic or loose objects). The BRIC technician will place the IV line while the participant is in the private prep room. The technician will then assist the participant in entering the PET/MR scanner. Once in the scanner, the BRIC technician will inject 555 MBq of the radiotracer through the IV during the scan. During the scan, the participant may receive a second injection of the radiotracer. The total amount of radiation exposure the subject will receive is about the same as they would normally receive in 12 months from natural background sources from the earth and sky. During a pre-scan training session, participants will learn that on each trial they can win the opportunity to earn a monetary reward and that if they don't win on a given trial, they will not earn a reward. During this pre-scan training session, participants will learn that one cue, a circle or a triangle (counter-balanced across participants), will signal that they may receive a reward and the other cue will signal that they will not receive a reward.

#### 4.3 SCIENTIFIC RATIONALE FOR STUDY DESIGN

This study and its design will deliver an empirically supported transdiagnostic anhedonia treatment as well as an fMRI-based quantitative index of mesocorticolimbic target engagement to use in future experimental therapeutics trials of novel anhedonia treatments. Testing whether the treatment impacts motivational circuitry specifically: The effects of many psychiatric treatments are non-specific.

Pharmacologic agents, including SSRI's, have relatively equivalent and moderate effects for a range of disorders [51], likely due to the fact that non-specific symptoms of general worry are targeted across disorders [52]. This proposal includes an fMRI task that is sensitive to the negative valence system construct of "threat" which includes anxious arousal, increased conflict detection, attentional bias to threat, and avoidance and recruits the amygdala, hippocampus, and insula. We will thus be able to distinguish the impact of BATA on brain systems that subserve motivation and pleasure from those that subserve threat. Aim 2 will include mid-treatment scans to determine the optimal BATA dose, and multilevel modelling will estimate the optimal number of sessions to achieve target engagement. In this way, we will be positional to evaluate the optimal dose of BATA in the R33 phase.

In the PET sub-study, because of the relatively slow kinetics of [11C]raclopride displacement, in the present study we will use a monetary incentive delay task that has been optimized for [11C]raclopride PET imaging (Schott et al., 2008). The task will be divided into rewarded (75% reward trials) and nonrewarded (0% reward trials) blocks that are each 18 minutes long.

#### 4.4 JUSTIFICATION FOR DOSE

Rationale for intended dose using BATA: The rationale for 15 sessions of BATA is based on our previous trials(MH094781 & MH078145) that indicate 15 sessions of behavioral activation for depression yielded clinical response in ~75% of patients with mood disorders and was sufficient to reduce anhedonia scores by ~40%.

